1.4.3. Regulatory Status – Australia

The PREVENA RESTOR™ Incision Management System is a Class IIa device licensed under ARTG318254 with the following indication for use.

The PREVENA RESTOR™ Incision Management System is intended to manage the environment of closed surgical incisions and surrounding intact skin in patients at risk for developing post-operative complications, such as infection, by maintaining a closed environment via the application of a negative pressure wound therapy system to the incision. The PREVENA RESTOR™ Incision Dressing skin interface layer with silver reduces microbial colonization in the fabric.

For those knees of subjects in this study that are randomized into the Treatment arm, the PREVENA RESTOR ARTHRO•FORM™ Incision Management System will be applied using the PREVENA PLUS™ 125 Therapy Unit (14-day) and a PREVENA RESTOR ARTHRO•FORM™ Dressing.

For this study, the PREVENA RESTOR™ Incision Management System will be used in accordance with its cleared labeling and indications for use. The system's indications, contraindications, warnings, precautions, and instructions can be found in the PREVENA RESTOR™ Incision Management System Instructions for Use (IFU) document.

2. STUDY OBJECTIVES

The primary objective of this study is to compare the effects of the PREVENA RESTOR ARTHRO•FORM™ Incision Management System to standard silver-containing dressings on lower limb swelling after bilateral primary total knee arthroplasty.

3. STUDY DESIGN

3.1. Design Summary

This randomized, controlled, prospective, global, multicenter study will enroll subjects undergoing simultaneous, bilateral, primary TKA. The study will enroll approximately 52 subjects (104 randomized knees) from approximately 10 sites. Each enrolled subject will receive ciNPT after surgery for one knee, and the other knee will receive a standard silver-containing post-surgical dressing.

The knee randomized to the ciNPT treatment arm will receive a PREVENA RESTOR ARTHRO•FORM™ Dressing in conjunction with the PREVENA PLUS™ 125 Therapy Unit for a duration of 12 to 14 days post-surgery, with a change of the PREVENA RESTOR ARTHRO•FORM™ Dressing at 5-7 days.

The knee randomized to the SOC treatment arm will receive a standard silver-containing dressing for 12-14 days with a dressing change and assessment at 5-7 days. Silver-containing dressings should be changed per the product IFU or as deemed necessary by the investigator or investigator-designated attending physician during the 12-14 day treatment period.

Subjects will be seen during Screening (no more than 42 days before TKA), on the day of surgery, one week after surgery (a minimum of 5 days to a maximum of 7 days), at 2 weeks after surgery (a minimum of 12 days to a maximum of 14 days post-surgery), at a 6-week follow-up visit (day 35 to 49), and at a 12-week follow-up visit (day 77 to 91). Subjects may participate in additional unscheduled visits as required during the study if

evaluation of either knee is required. Unscheduled visits may be initiated by either the investigator or the subject.

3.1.1. PREVENA RESTOR ARTHRO•FORM™ Dressing

Closed incision NPT will be applied to the clean, closed surgical wound immediately following closure and randomization. The dressing will be applied on Day 0 and changed on post-surgical Day 5-7. Closed incision NPT will be discontinued, and the dressing will be removed by Day 14.

3.1.2. Standard silver-containing dressing

Standard silver-containing dressings will be applied to the clean, closed surgical wound immediately following closure and randomization. The dressing will be applied on Day 0 and changed on Day 7 or as deemed necessary by the investigator (or investigator designee). If subsequent dressings are applied, the final dressing must be removed by Day 14.

3.1.3. Duration of Study Participation

The duration of study participation for each subject is as follows:

- Screening Period: up to 42 days (Day -42 to Day 0)
- Day of Surgery - Bilateral TKA procedures
- Treatment Period: 2 weeks (12-14 days, but no longer than 14 days), with dressing change and assessment at 1 week (5-7 days)
- Follow-up: 6 weeks (\pm 1 week) and 12 weeks (\pm 1 week) after bilateral TKA

The maximum participation duration per subject is up to 134 days.

3.2. Primary Endpoint

The primary endpoint is the percent change in lower limb volume, as calculated based on manual circumference measurements, 5-7 days after bilateral TKA when using the PREVENA RESTOR ARTHRO•FORM™ Incision Management System compared to the control.

3.3. Secondary Endpoints

The secondary endpoints are as follows:

- Percent change in lower limb volume, as calculated based on manual circumference measurements, from baseline to visits 4, 5, and 6
- Percent change in circumferences from baseline to visits 3-6 that are measured at:
 - 10 cm above the center of the patella
 - at the center of the patella
 - 10 cm below the center of the patella
 - at the ankle; 1 cm above the medial malleolus
- Change in knee flexion angle from baseline to visits 3-6
- Change in knee extension angle from baseline to visits 3-6
- Change of total ROM degrees, defined as the flexion angle minus the extension angle, from baseline to visits 3-6
- The incidence of SSCs by visits 5 and 6
- Scar cosmesis assessment at visits 3-6
- The average pain in each leg in the last 24 hours, using an NPRS (numerical pain rating scale) of 0-10 (daily for 4 weeks post-surgery, then weekly for weeks 5-12)
- The worst pain in each leg in the last 24 hours, using an NPRS of 0-10 (daily for 4 weeks post-surgery, then weekly for weeks 5-12).

3.4. Exploratory Endpoints

The exploratory endpoints are as follows:

- the percent change in lower limb volume, as calculated based on three-dimensional (3D) imaging, from baseline to visits 3-6

- Knee-related QoL questionnaire (new Knee Society Knee Scoring System) at visits 4, 5, and 6
- Ability to perform a straight leg raise at visits 4, 5, and 6

Additional exploratory endpoints may be added and will be detailed in the statistical analysis plan (SAP).

3.5. Health Economic Endpoints

The health economic endpoints are as follows:

- Total length of hospitalization
- Subsequent emergency department (ED) visits related to either knee and reason (eg, edema or pain)
- Subsequent hospitalization related to either knee and reason (eg, edema or pain)
- Subsequent clinic visits (unscheduled) related to either knee and reason (eg, edema or pain).

Additional health economic endpoints may be added and will be detailed in the statistical analysis plan (SAP).

3.6. Safety Endpoint

The Safety Endpoint is the incidence of Adverse Events and Serious Adverse Events, including subsequent emergency department visits or subsequent hospitalizations/interventions for either knee.

4. STUDY PROCEDURES AND ASSESSMENTS

4.1. Informed Consent

The investigator, or designee, will discuss the purpose of this study with potential subjects. Each individual will review the Informed Consent Form (ICF) approved by the local Institutional Review Board (IRB) or Ethics Committee (EC). The ICF must be signed

according to IRB/EC requirements before the subject can undergo any study-related procedures. Informed consent will be obtained under these conditions:

- Subjects must be made aware of the purpose of the study and the potential risks and benefits known or that can be reasonably predicted or expected in language that is understandable to the subject.
- Subjects must be given the opportunity to ask the investigator questions and must be provided time to consider participation in the study.
- ICFs will be written in a manner that is non-technical and understandable to the subject.
- Subjects will not be led to believe that they are waiving their legal rights to release the investigator, sponsor, study site, or any of their agents from liability for negligence.
- Subjects will be asked to sign and date the ICF indicating their informed consent to participate in the study.
- The investigator's responsibilities during the ICF process include:
 - screening out potential subjects who may not be able or willing to comply with the study protocol.
 - discussing with potential subjects to ensure they understand the purpose of the study, the study procedures that will be required, and the risks and benefits known or that can be reasonably predicted or expected.
 - answering all questions from potential subjects.
 - ensuring that subjects have signed the ICF before undergoing any study-related assessments.
 - confirming that the study-site representative performing the informed consent process has signed the informed consent form, if required.
 - ensuring that each subject receives a copy of the signed ICF.

4.2. Inclusion/Exclusion

In order to be considered for randomization, a subject must meet all eligibility criteria and be assessed no more than 42 days before surgery. Subjects who do not meet all eligibility criteria will not be eligible for randomization, will discontinue from the study, and will be considered a screen failure. Inclusion and exclusion criteria will be reconfirmed immediately prior to surgery if visit 1 and visit 2 are on different dates.

4.2.1. Inclusion Criteria

The subject:

- is at least 22 years of age on the date of informed consent.
- can independently provide informed consent.
- requires and is scheduled to undergo a simultaneous, bilateral, primary TKA.
- is willing and physically capable of undergoing a simultaneous, bilateral, primary TKA with or without replacement of the patella.
- is willing and able to return for all scheduled study visits.

4.2.2. Exclusion Criteria

The subject:

- is pregnant or lactating.
- has signs of an infection in the area of either knee or has signs of a systemic infection at the time of surgery.
- is a chronic opioid user, defined per the CDC guidelines as opioid use for >3 months, at the time of enrollment.
- has a current diagnosis of lymphedema in either leg
- has signs, symptoms, or a current diagnosis of venous insufficiency in either leg, as determined by the investigator's review of the subject's medical history.
- has a history of clotting disorder or prior history of deep vein thrombosis

- will undergo a unilateral TKA
- will undergo a staged, bilateral TKA
- has received a corticosteroid injection into either knee within 30 days of surgery
- undergoes a simultaneous, bilateral TKA with a planned different incision type on each knee (eg, midline incision vs. medial parapatellar incision).
- has known sensitivity to the study product components (drape and/or dressing materials in direct contact with the closed incision or skin).
- has known sensitivity to silver.
- is enrolled in another interventional clinical study.
- has skin cancer localized at or in proximity to the incision site.
- does not have access to an electronic device (smartphone, iPad, or computer) on a daily basis to complete online assessments.
- has condition(s) that, in the opinion of the investigator, cause the subject to be an overall health risk that is unsuitable for the surgery.
- has condition(s) that, in the opinion of the investigator, will impact study endpoints (eg, hemophilia or autoimmune disorders) or the ability to comply with study procedures.

4.2.3. Intra-Operative Exclusion Criteria

Randomization occurs immediately after completion of the first total knee arthroplasty surgery. Prior to randomization, the following criteria should be assessed to determine if randomization should occur or the subject becomes a screen failure.

The subject:

- does not receive a “total” knee replacement for first knee. For example, a partial or uni-compartmental knee replacement is performed

- has a surgical incision that would preclude placement of either dressing onto the knee
- has a TKA resulting in a muscle flap

4.3. Premature Study Termination

If the study is terminated prematurely or suspended, study subjects and the IRB/EC will be informed promptly and provided with the reason(s) for the termination or suspension by the sponsor or by the investigator. If applicable, regulatory authorities and the personal physicians of the subjects will also be informed.

4.3.1. By Sponsor

The sponsor reserves the right to discontinue the clinical study for business or ethical reasons at any time, such as, but not limited to:

- Information regarding the study product causes doubt as to the benefit/risk ratio.
- Changes in medical practice limit utility of the data obtained from the study.

The sponsor reserves the right to terminate a study at a site at any time, including but not limited to any of the following reasons:

- Investigator(s) lack of compliance with the approved study protocol, lack of oversight, and/or not following applicable regulatory or IRB/EC guidelines in conducting the study
- Incidence or severity of AEs indicates a potential health hazard or poses an unreasonable risk to the study participants
- Subject enrollment is unsatisfactory
- Fraud or misconduct

4.3.2. By IRB/EC

The IRB/EC may choose to discontinue the study at the site for which they granted approval. If the IRB/EC discontinues the study, the investigator will report a withdrawal of IRB/EC approval to the study sponsor within five (5) working days.

4.4. Subject Withdrawal or Termination

4.4.1. Reasons for Withdrawal or Termination

Subjects may withdraw from participation in the study at any time upon request.

The investigator may choose to terminate the participation of a subject from the study with or without their consent for any of the following reasons:

- Adverse events
- Noncompliance
- For any reason that may, in the opinion of the investigator, negatively affect the safety or well-being of the subject

Subjects with the following surgical outcomes will be withdrawn from the study.

- Subject does not undergo a bilateral TKA procedure
- Subject does not receive a “total” knee replacement for each knee. For example, a partial or uni-compartmental knee replacement is performed on one or both sides
- Subject has a surgical incision that precludes placement of either dressing onto the appropriately randomized knee
- Subject has a TKA resulting in a muscle flap

An investigator must terminate participation of a subject from the study for any of the reasons indicated in section 4.17.

4.4.2. Handling of Withdrawal or Termination

Every effort should be made to complete assessments required for the primary endpoint and safety endpoints prior to the subject withdrawal.

For subjects who are lost to follow-up, the investigator will make attempts to collect at least the vital status (eg, whether the subject is alive) before formally withdrawing the subject from the study. Prior to considering a subject lost to follow-up, at least two documented attempts should be made to contact the subject through all available routes, and a certified letter should be sent to the permanent address on file.

Once the subject withdraws from the study, both knees will be considered withdrawn. A subject may not withdraw only one knee from the study. No further study evaluations will be performed, and no additional data will be collected. The investigator may retain and continue to use any data collected before withdrawal. The subject will not be replaced.

If for any reason the subject is withdrawn by the investigator from this study, the investigator will inform the subject and the sponsor.

4.5. Demographics and Subject Characteristics

The following demographic data and subject characteristics will be collected and documented after the subject signs the ICF:

- Age
- Sex
- Race / Ethnicity
- Vital signs (height/weight)
- Comorbidities

4.6. Medical and Surgical History

The research staff will collect medical and surgical history for each subject. If the screening visit and surgery occur on different days, the medical and surgical history will be updated (if changes have occurred) at the surgical visit.

4.7. Laboratory Assessment for Pregnancy

Serum or urine assessment for human chorionic gonadotropin (hCG) to determine pregnancy status in female subjects of child-bearing potential will be conducted. This

assessment will need to be captured on the day of surgery. If the pregnancy test is positive, the subject will not be eligible for the study and will be considered a screen failure. Women who have had documented surgical sterilization by a medically accepted method (eg, tubal ligation, hysterectomy, or oophorectomy) or are post-menopausal, defined as not having menstruation for > 12 months, will be excluded from this laboratory assessment.

4.8. Randomization and Subject Numbering

Consented subjects will be assigned a unique subject identifier. Study data will be reported according to this unique subject identifier.

Subjects who satisfy all inclusion criteria and none of the exclusion criteria will be eligible for randomization, which will occur upon closure of the first knee in the bilateral procedure. Randomization of each knee to the treatment arm or the control arm will be centralized, electronic, and web-based.

If a screened subject does not meet all inclusion criteria or meets any exclusion criteria, the subject will be considered a screen failure.

4.9. Lower Limb Volume

Lower limb volume for each leg will be calculated using two different methods. The first will be the Partial Frustum Model method³¹, using measurements of circumference taken above and below the patella. The circumferences of each limb will be measured at the center of the patella, every 5 cm from the center of the patella to 15 cm superior to the patella (ie, 3 measurements), every 5 cm from the center of the patella to 20-30 cm inferior to the patella (ie, no less than 4 but no more than 6 measurements). Additionally, the circumference 1 cm above the superior edge of the medial malleolus will also be measured for each leg; however, the measurement taken 1 cm above the malleolus should not overlap with the most inferior measurement taken below the patella. There will be a total of nine (9) to 11 measurements per leg. The volume of each leg segment (between two measures of circumference) will then be calculated using a formula for a

truncated cone, and the sum of all segments will then be calculated to determine lower limb volume.

The second method for calculating lower limb volume will utilize a mobile 3D imaging system (LymphaTech) that combines an infrared depth sensor with a tablet computer using proprietary software. 3D imaging will be performed by the investigator or investigator designee according to the User Guide documentation that accompanies the tablet computer that is provided to the investigators. Briefly, the subject will stand with their feet shoulder-width apart on a flat surface with an approximately 1 meter radius of free space on all sides. The investigator will then scan both legs by slowly walking around the subject while keeping the camera pointed at the subject and moving the camera up and down to capture a 3D rendering (ie, image) of the entirety of both legs. During the scan, the subject should remain as still as possible, and the lower limbs should be free of any materials that will distort the image (eg, clothing covering the area). Once the 3D rendering is obtained and inspected for quality, lower limb volume will be calculated using scan measurements from the mid-thigh to the ankle of each leg, excluding the gluteal fold region of each leg, the heel/ankle region of each leg, and the feet.

4.10. Knee Range of Motion

ROM is the full movement of the joint, measured as an increased or decreased angle (ie, degrees) between the bones of the limb at the joint. ROM for the knee includes flexion (bending) and extension (straightening). A completely straight knee will have a joint measure of 0° while a fully bent knee (without crouching) will have about 135° of flexion. For this study, the flexion and extension angles of each knee will be captured using a goniometer with the subject lying flat, in the supine position. ROM will be calculated as the difference between the flexion angle and the extension angle. Both active ROM, whereby the subject flexes and extends the joint without assistance, and passive ROM, whereby the investigator or investigator designee flexes and extends the joint, will be captured.

4.11. Patient Reported Outcomes (PRO) Assessment: Knee Society Knee Scoring System (KSKSS)

The KSKSS is a validated system that combines an objective physician-derived component with a subjective patient-derived component to evaluate pain relief, functional abilities, satisfaction and fulfillment of expectations. The score prioritizes the patient perspective to better track patient expectations, satisfaction, and activity levels. Two variations of the form exist: a preoperative evaluation completed prior to surgery and a postoperative evaluation administered after surgery.³²

Aside from a section on demographics, the questionnaire is divided into 4 scoring sections:

1. Objective components consisting of:
 - Alignment
 - Instability
 - Joint Motion
 - Symptoms
2. Patient expectations
3. Patient satisfaction
4. Functional components consisting of:
 - Walking and Standing
 - Standard Activities
 - Advanced Activities
 - Discretionary Activities

In this study, each knee will be independently scored using the KSKSS.

4.12. Pain Assessments

Pain will be captured daily for the first 4 weeks post-surgery and then weekly for weeks 5-12. In addition, a baseline pain assessment associated with each knee will be captured at screening and recorded by the investigator or investigator designee. After surgery, the pain associated with each leg will be electronically recorded using an ePRO system as part of the EDC. Subjects will receive reminders (eg, phone calls, e-mails, or ePRO system reminders) to log-in by computer or use an app to complete their pain assessments.

For all pain assessments, subjects will evaluate their average pain and their worst pain associated with each leg for the previous 24hr period using the numerical pain rating scale (NPRS), which ranges from 0 (no pain) to 10 (extremely painful).

4.13. Surgical Procedures and Assessments

4.13.1. Bilateral TKA Procedure

The surgical procedure will be performed in accordance with the investigator's standard practice; however, the incision type for each knee should be the same. For the method of closure, types such as sutures, staples, steri-strips, and skin glue are allowed; however, skin closure using any type of plastic closure device (eg, Zipline sutures) is restricted. The following information regarding the TKA procedure will be documented:

- Order of knee surgery (right vs. left)
- Administration of tranexamic acid preoperatively or intraoperatively
- Surgical approach
- Method of Closure (each knee)
- Length of incision
- Anesthesia start and stop time

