5. VISIT SCHEDULE AND DESCRIPTION OF STUDY VISITS

5.1. Schedule of Visits

Procedure Description	Visit 1	Visit 2			Visit 3 Mid-Treatment Follow-up	Visit 4 End of Treatment	Visit 5 Midterm Follow-up	Visit 6 Long Term Follow-up	Unscheduled
	Screening	Pre-Op	Intra-Op	Post-Op					
Visit Windows	Day -42 to 0	Day 0	Day 0	Day 1	Day 5-7	Day 12-14	Day 35-49	Day 77-91	
Informed Consent	X								
Inclusion/Exclusion Criteria	X	X ¹							
Demographics and Subject Characteristics	X	X ¹							
Medical and Surgical History	X	X ¹							
Knee Society Knee Score	X				X	X	X	X	X
Lower Limb Volume – Circumference measurements (manual and 3D)		X			X	X	X	X	X
Range of Motion		X			X	X	X	X	X
Pain Assessment		X		X ⁴					X
Laboratory Assessment for Pregnancy		X ²							
Bilateral TKA Procedure			X						
Intra-op exclusion criteria			X						
Randomization			X ³						

Procedure Description	Visit 1	Visit 2			Visit 3 Mid- Treatment Follow-up	Visit 4 End of Treatment	Visit 5 Midterm Follow-up	Visit 6 Long Term Follow-up	Unscheduled
	Screening	Day of Surgery							
		Pre-Op	Intra-Op	Post-Op					
Visit Windows	Day -42 to 0	Day 0	Day 0	Day 1	Day 5-7	Day 12-14	Day 35-49	Day 77-91	
Application of Treatment			X						
Concomitant Medication			X	X	X	X	X	X	X
Adverse Events			X	X	X	X	X	X	X
Removal of Study Treatment					X ⁵	X			
Scar cosmesis assessment					X	X	X	X	X
Straight Leg raises					X	X	X	X	X
Health Economic Assessments					X	X	X	X	X
SSC Assessments					X	X	X	X	X
End of Study								X	X ⁶

¹ If visit 1 and visit 2 occur on different days, assessments will be reviewed and updated if changes have occurred.

² For women of child-bearing potential

³ Upon surgical closure of 1st TKA but before initiating 2nd TKA on the contralateral knee.

⁴ Daily post-op pain collection will start the day following bilateral TKA by ePRO.

⁵ Dressings will be removed, and a new dressing placed after assessments completed.

⁶ If the subject is withdrawn early.

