8.2.4. Analysis of Primary Endpoint

The primary endpoint is the percent change in lower limb volume, as calculated based on manual circumference measurements, 5-7 days after total knee arthroplasty (TKA) when using the PREVENA RESTOR ARTHRO•FORM™ Incision Management System

compared to the control. The lower limb volume is calculated using the Frustum formula^{35;36}:

$$Volume = \sum \pi(x_{(i+1)}^2 + x_i^2 + x_i \cdot x_{(i+1)}) \left(\frac{h}{3}\right)$$

where x_i and x_{i+1} are the circumferences of two consecutive sections along the limb, and h is the length of the interval between the two measurements on the limb. The lower limb volume is determined by calculating the sum of the volumes of all sections. The percent change of the lower limb volume is defined as the difference of lower limb volume from baseline (pre-op) to postoperative Day 5-7, divided by the baseline measurement of lower limb volume, multiplied by 100.

A general linear mixed model repeated measures analysis (MMRM) will be used to analyze the primary endpoint with covariates: site, study visit, treatment, knee side (left/right), baseline lower limb volume, baseline BMI category ($<30 \text{ kg/m}^2$, $\geq 30 \text{ kg/m}^2$), and treatment by study visit. Knee side will serve as a repeated-measure factor to account for the correlations between left knee and right knee on the same subject, and the subject variable will also be specified to identify those observations that are to be correlated. Raw means, LS Means, including 95% confidence intervals, will be presented by treatment group. The ITT analysis set will be used for the primary analysis.

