8.2.4.1. Sensitivity Analyses of Primary endpoint

- The primary analysis will be repeated on the Per-Protocol analysis set.
- The primary analysis will be repeated on the ITT analysis set to explore the following covariate: treatment, site, visit, baseline lower limb volume, surgical approach, and length of incisions.
- Additional sensitivity analyses may be conducted to explore other characteristics that may impact the lower limb volume. All analyses will be outlined in the Statistical Analysis Plan.

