8.3. Additional Statistical Details

8.3.1. Sample Size Determination

Pichonnaz et al measured the limb volume utilizing the truncated cone method. The mean volume percentage difference from baseline to Day 8 post-surgery was 11.9%, with a standard deviation of 8.2% at Day 8.¹ In 2016, Pichonnaz et al used the same method to evaluate the lower limb volume and the mean percentage difference from baseline to postoperative Day 7 was 15.3%, with a standard deviation of 6.5% at Day 7.² Assuming in our study the control group has a percent change of 13.6% in volume from baseline to post-surgery Day 6-8, while the PREVENA RESTOR group holds a percent change of 8% in the same period, given the standard deviation is 9.2% in both groups, a total of **52**

subjects (assuming 15% dropout rate) are needed to achieve 80% power based on a two-sample t-test with a type I error rate of 0.05.

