8.3.2. Randomization

All subjects who meet all inclusion criteria and no exclusion criteria will be randomized in a 1:1 ratio to receive the PREVENA RESTOR ARTHRO•FORM™ Incision Management System or the control in either right or left knee. Each subject will receive both treatments (one treatment per knee). A randomization schedule, including randomization numbers and treatment assignments, will be generated and maintained centrally in the web-based clinical database management system. Once randomized, a subject's assignment cannot be altered or changed; a subject should not be randomized twice. The randomization schedule will be kept blind to any person who is involved in the daily operations of the study. It will only be accessible to the study biostatisticians who generate and review the schedule, and the vendor's team members (if an EDC vendor is utilized) who are involved in reviewing the schedule and uploading the schedule.

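### Surgical order (first or second knee) is recorded and fixed before randomisation but is in neither the primary model nor the named sensitivity model, at a modest cost in precision

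*Combined protocol and SAP*

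**What the plan says.** Section 4.13.1 lists "Order of knee surgery (right vs. left" among the items documented for every procedure.

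The timing of allocation is stated consistently. Section 4.2.3: "Randomization occurs immediately after completion of the first total knee arthroplasty surgery". The schedule footnote in section 5.1: "Upon surgical closure of 1st TKA but before initiating 2nd TKA on the contralateral knee". Section 4.8 agrees. Which knee is first is therefore settled before the arm is known.

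Section 8.3.2 allocates subjects 1:1 to the study device "or the control in either right or left knee". It states no stratification or balancing by surgical order.

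The primary MMRM in section 8.2.4 is specified "with covariates: site, study visit, treatment, knee side (left/right), baseline lower limb volume", followed by BMI category and treatment by visit. The sensitivity model in section 8.2.4.1 uses "treatment, site, visit, baseline lower limb volume, surgical approach, and length of incisions". Order is in neither, and no other section uses it in an analysis. Section 8.2.4.1 leaves room for further, unspecified sensitivity analyses, and section 8.6 defers full detail to a SAP to be finalised before database lock.

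**The concern.** Each subject supplies one knee to each arm, so the treatment effect is estimated from the difference between a subject's two knees. Site and BMI category take the same value for both knees and, as main effects, cannot sharpen that difference. Covariates that differ between the knees can: knee side and baseline volume, which are in the model, and surgical order, which is not.

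If the first and second knees tend to swell differently, that difference goes into the residual of the between-knee contrast and widens the interval for the primary comparison. Order is already collected and cannot be affected by treatment, so adjusting for it is safe.

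**Working it through.** **Inputs from the documents.** Control mean: the "control group has a percent change of 13.6% in volume" (section 8.3.1). Device mean 8%, so the target difference is 13.6 − 8 = 5.6 points. SD 9.2 in both groups, 15% dropout, 80% power, two-sample t-test (section 8.3.1). Two-sided 0.05 (section 8.2.1).

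**The plan's own figure.** The normal approximation gives 2 × (1.96 + 0.8416)² × 9.2² / 5.6² = 42.4, so 43 per arm. The noncentral t calculation gives 44 per arm with power 80.6%. 44 / 0.85 = 51.8, so 52 subjects. The stated 52 is reproduced, and about 44 evaluable pairs are used below.

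**Assumed, because the documents are silent.** An order effect g (first minus second knee, in percentage points) of 0 to 3; a between-knee correlation ρ of 0.5 to 0.7; simple randomisation; and right-first and left-first surgery equally common. The SD of 9.2 is taken to include any order contribution. The calculation is for the between-knee difference at one visit.

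**Model.** Device knee minus control knee = treatment effect + g × O + error, where O = +1 if the device knee was operated on first and −1 otherwise. The variance of the difference is 2 × 9.2² × (1 − ρ), which is 84.64 at ρ = 0.5 and 50.78 at ρ = 0.7. Order contributes g², so its share is g² divided by that variance. Adjustment multiplies the interval width by about √(1 − share), ignoring the one degree of freedom spent.

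| g (points) | Share, ρ = 0.5 | Share, ρ = 0.7 | SE without → with order, ρ = 0.5 | SE without → with order, ρ = 0.7 |
|---|---|---|---|---|
| 0 | 0% | 0% | 1.387 → 1.387 | 1.074 → 1.074 |
| 1 | 1/84.64 = 1.2% | 1/50.78 = 2.0% | 1.387 → 1.379 | 1.074 → 1.064 |
| 2 | 4/84.64 = 4.7% | 4/50.78 = 7.9% | 1.387 → 1.354 | 1.074 → 1.031 |
| 3 | 9/84.64 = 10.6% | 9/50.78 = 17.7% | 1.387 → 1.311 | 1.074 → 0.974 |

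At 3 points the interval narrows by 1 − √0.894 = 5.5% (ρ = 0.5) or 1 − √0.823 = 9.3% (ρ = 0.7).

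**Effect on power.** At ρ = 0 and g = 2, power goes from 79.7% to 80.5%. At ρ = 0.5 it is 97.6% without the term. With no order effect the term costs about 0.1 point of power or less.

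**What knee side already absorbs.** If a share q of subjects have the right knee done first, the order variance left after adjusting for side is 4q(1 − q): 100% at q = 0.5, 64% at q = 0.8 (4 × 0.8 × 0.2) and 0% at q = 1. The table is therefore the upper end; the documents do not give q.

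**Treatment by order.** Every subject has one first and one second knee, so this interaction is the difference in two-knee totals between the device-first and control-first groups, about 22 and 22 subjects. Its SE is √[2 × 9.2² × (1 + ρ)] × √(2/22), which is 15.93 × 0.3015 = 4.8 at ρ = 0.5 and 16.96 × 0.3015 = 5.1 at ρ = 0.7, before covariate adjustment. For 80% power the interaction would have to be about 2.80 × 4.8 = 13.4 to 2.80 × 5.1 = 14.3 points, more than twice the 5.6-point target.

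**The case against.** The strongest reply is that nothing in the plan is wrong. Allocation is random given order, so the unadjusted contrast is unbiased and its interval valid, and a precision covariate is the analyst's choice. That stands. A reader might infer that leaving order out biases the result; the documents do not support this.

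A reader might also count chance imbalance as a second harm. A split of 27:17 or worse has probability 0.174 under simple randomisation with 44 pairs, and it moves the unadjusted estimate by (27 − 17)/44 = 0.227 points per point of order effect. But this is the same loss seen from another side. At g = 2 the variance of the chance shift is 4/44 = 0.091, which is the drop in squared SE at ρ = 0.5 (1.387² − 1.354² ≈ 0.09). The unadjusted interval already carries it.

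The size rests on an order effect that no section documents, and an effect of 0 or 1 point leaves almost nothing to gain. The sample size was set by a two-sample test, so a positive between-knee correlation already gives the paired analysis power to spare. Knee side may absorb some or all of the effect, so it would be too strong to say that it does nothing in place of order. All of this stands and limits the weight of the point.

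The remaining reply, that the later SAP may add order, is only partly met by the text. Section 8.2.4.1 leaves room for extra sensitivity analyses, but the primary covariate list is already given without order.

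**Conclusion.** The point holds as a small, nearly free improvement in precision. Order is recorded, fixed before randomisation, and absent from the primary and the named sensitivity models. Under the stated assumptions it takes up between 0% (no order effect) and 11–18% (3 points) of the within-pair variance, at most about a 5–9% change in interval width, and less where one side is habitually done first. A single order term recovers this in full only if the effect is similar across visits. The sample size is not called into question.

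One further inference should be resisted. The second knee is operated on after the arm has been generated, so a reader might propose treatment-by-order as a check that this knowledge is harmless. With an SE of about 4.8–5.1 points, a null result could not give that reassurance, and an order main effect does not address the question.

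**What to change.** Add surgical order (first or second knee operated on) as a fixed covariate in the primary MMRM (synopsis and section 8.2.4) and in the secondary MMRMs (section 8.2.5, including the weekly pain model, which has its own covariate list). Keep knee side. Order per knee follows directly from the recorded order and the side. Write it into the SAP before any outcome data are summarised by arm, so that it cannot look like a response to an observed imbalance.

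If treatment-by-order is reported, label it descriptive, state its expected SE, and do not offer it as evidence about knowledge of the arm during second-knee surgery.

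Cost: a line of SAP wording, one degree of freedom per model, no new data and no change to trial conduct.
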